6.2 Randomization

Participants will first be randomized in a 1:1:1 ratio into the Part A sentinel safety cohort. If safety criteria are met, enrollment will proceed with Part B sentinel group of n=12 with 1:1:1 randomization and the remainder of Part A (n=42) with 1:1:1 randomization, with some sites enrolling into the Part B sentinel cohort while other sites are enrolling the remainder of Part A. Once the safety criteria for the Part B sentinel safety cohort have been met, the remaining Part B participants (n=42) will be enrolled with 1:1:1 randomization.

Randomization to Groups 1-3 will be stratified by willingness to consent to FNA and/or leukapheresis. A maximum of 27 participants in total that do NOT consent to either FNA and leukapheresis collection will be enrolled.

A participant's randomization assignment will be computer generated and provided to the HVTN CRS pharmacist through a web-based randomization system. At each institution, the pharmacist with primary responsibility for dispensing study products is charged with maintaining security of the treatment assignments (except in emergency situations as specified in the HVTN Manual of Operations [MOP]).

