3.2 Secondary objectives and endpoints

Secondary objective 1:

To evaluate the ability of BG505 MD39.3 trimer mRNA vaccines to elicit humoral and cellular immune responses and to compare responses between the membrane-bound vaccine regimen (BG505 MD39.3 gp151 mRNA) and the membrane-bound knockout (BG505 MD39.3 gp151 CD4KO mRNA) and between the membrane-bound vaccine regimen (BG505 MD39.3 gp151 mRNA) and the soluble trimer (BG505 MD39.3 mRNA) vaccine arms, within each dose level and to compare responses between dose levels for each vaccine regimen

Secondary endpoints 1:

- Occurrence, magnitude, and response rate of serum antibody neutralization of a vaccine-matched tier 2 HIV-1 strain as measured by the TZM-bl assay two weeks after the second vaccination
- Occurrence, magnitude, and response rate of serum IgG binding antibodies to the BG505 trimer, and specific epitopes (base of trimer, V3, internal epitope) as measured by binding antibody multiplex assay (BAMA) two weeks after the second and third vaccination
- Occurrence, magnitude, and response rate of CD4+ T-cell responses as assessed by intracellular cytokine staining assays (ICS) two weeks after the third vaccination

Secondary objective 2:

To evaluate the durability of humoral immune responses to BG505 MD39.3 trimer mRNA vaccines and to compare durability between arms

Secondary endpoints 2:

- Occurrence, magnitude, and response rate of serum antibody neutralization of a vaccine-matched tier 2 HIV-1 strain, as measured by the TZM-bl assay six months after the third vaccination
- Occurrence, magnitude, and response rate of serum IgG binding antibodies to the BG505 trimer, and specific epitopes (base of trimer, V3, internal epitope), as measured by BAMA six months after the third vaccination

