analysis consists of 4 individual tests comparing the membrane-bound vaccine regimen (BG505 MD39.3 gp151 mRNA) to the membrane-bound knockout (BG505 MD39.3 gp151 CD4KO mRNA) and to the soluble trimer (BG505 MD39.3 mRNA) vaccine arms within each dose level, unless prespecified. That is, we compare Groups 2 vs 1, Groups 2 vs 3, Groups 5 vs 4, and Groups 5 vs 6. Secondary analyses will compare responses between dose levels for each regimen. If no differences are seen between dose levels for a given vaccine regimen, subsequent comparisons of that vaccine regimen may be based on the aggregated arms (eg, pooling over dose). If rank-based tests are used, then the tests will be inverted to construct Hodges-Lehmann point estimates and 2-sided $(1-0.05/15) \times 100\%$ CIs about the differences in location centers of the 3-15 pair-wise comparisons of vaccine arms. If actual-value tests are used then the Dunnett's procedure will be used to construct simultaneous confidence intervals about the pairs of mean differences for the many-to-one comparisons (42) when multiple vaccine arms are each compared with one common control arm. When all pair-wise comparisons between the multiple vaccine arms are of interest, the Tukey procedure (43) will be used. If only specific comparisons between pairs of the multiple vaccine arms are of interest, the Holm-Bonferroni procedure will be used. An appropriate data transformation (eg, \log_{10} transformation) may be applied to better satisfy assumptions of symmetry and homoscedasticity (constant variance). Significance of the differences between pairs will be evaluated using two procedures, first based on whether the simultaneous 95% CIs exclude zero and secondly based on whether the nominal (unadjusted) 95% CIs exclude zero.

Some immunologic assays have underlying continuous or count-type readout that are dichotomized into responder/nonresponder categories (eg, BAMA, TZM-BL). If treatment arm differences for these assays are best summarized by a mixture model, then either Lachenbruch's test statistic (44) or an alternative two-part test (45) (as defined in the SAP) will be used to evaluate the composite null hypothesis of equal response rates in the 2 arms and equal response distributions.

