9.6 Sentinel Safety Reviews

Enrollment will start with Groups 1-3 simultaneously until a total of 12 participants, approximately 4 participants in each group (Part A sentinel safety cohort) have been enrolled. Enrollment will then pause. The PSRT will review cumulative safety information recorded through the safety visit scheduled two weeks post first vaccination and will determine whether it is safe to proceed with enrolling the participants in Groups 4-6 and the rest of Groups 1-3.

Enrollment will then start again for the first 12 participants in Groups 4-6 (Part B sentinel safety cohort) and the rest of Part A (Groups 1-3) in parallel. Once the Part B sentinel safety cohort (Groups 4-6) has been fully enrolled, enrollment in Groups 4-6 will then pause while the remainder of Part A (Groups 1-3) continues enrollment. The PSRT will review cumulative safety information recorded for Groups 4-6 (Part B sentinel safety cohort) through the safety visit scheduled two weeks post first vaccination and will determine whether it is safe to proceed with enrolling the remainder of participants in Groups 4-6 (see also [Section 6.1](#)). As PSRT safety reviews are performed weekly during the vaccination phase ([Section 9.4.1](#)), this review will also automatically include cumulative safety data from Part A participants available at this time.

This enrollment and safety review strategy allows for a single enrollment pause whilst maintaining separate randomization schemas for Part A and Part B participants. Additionally, this strategy allows for intervention of enrollment and vaccination plans for the higher dose group if safety concerns are identified in either Part A participants or the sentinel safety cohort of Part B.

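### The 100 vs 250 mcg comparisons are not randomised but are tested as ordinary two-sample contrasts, and pooling over dose for one regimen only would carry half of any Part difference into an immunogen contrast

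*Protocol*

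**What the plan says.** Protocol section 9.6 describes the enrolment strategy as "maintaining separate randomization schemas for Part A and Part B participants". The Part A sentinel group (12) enrols first. After its review, the Part B sentinel group (12) and the rest of Part A (42) enrol in parallel, "with some sites enrolling into the Part B sentinel cohort while other sites are enrolling the remainder of Part A" (section 6.2). Then "enrollment in Groups 4-6 will then pause while the remainder of Part A (Groups 1-3) continues enrollment" (section 9.6). After the Part B sentinel review, "the remaining Part B participants (n=42) will be enrolled with 1:1:1 randomization" (section 6.2).

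Section 6.2 adds two features that belong to Part A: "Randomization to Groups 1-3 will be stratified by willingness to consent to FNA and/or leukapheresis", and "A maximum of 27 participants in total that do NOT consent to either FNA and leukapheresis collection will be enrolled". Section 8.5 confines both procedures to Groups 1-3.

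Secondary objective 1 includes the aim "to compare responses between dose levels for each vaccine regimen" (section 3.2), and section 6.3.4.1 repeats it: "Secondary analyses will compare responses between dose levels for each regimen". That section tests differences between arms with a Wilcoxon rank sum or two-sample t-test, and response rates with Barnard's or Fisher's test. If a regimen shows no dose difference, its later comparisons may use the arms combined over dose. Section 6.1.1 applies its 11-fold power statement to two dose levels as well as to two groups.

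**The concern.** Nobody is allocated at random between 100 and 250 mcg. Groups 1 vs 4, 2 vs 5 and 3 vs 6 therefore differ in dose and in whatever else differs between the Parts: enrolment period, possibly site mix, and possibly the kind of volunteer. A two-sample p-value attributes all of that to dose, and a Part difference could create an apparent dose effect or hide a real one.

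The result also steers a later step. A non-significant dose test permits pooling, and the condition is stated for each regimen separately. If one regimen is pooled and its comparator is not, an immunogen contrast that was protected by randomisation within Part becomes partly a contrast between Parts.

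**Working it through.** **Which contrasts cross Parts**

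- Primary: 2 vs 1, 2 vs 3, 5 vs 4, 5 vs 6. All within one Part and randomised.
- Secondary dose contrasts: 1 vs 4, 2 vs 5, 3 vs 6. All cross Parts and are not randomised.
- Both regimens pooled, for example 1+4 vs 2+5 (the example in section 6.1.1). Each side has about 15 from each Part, so an additive Part shift cancels.
- One regimen pooled, for example 2+5 (30) vs 1 (15). With Part B higher than Part A by b, the pooled mean is raised by (0 + b)/2 = b/2 and the comparator by 0, so the bias is b/2. A true dose effect enters in the same way.

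**How far sites can differ**

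The split is stated for the parallel phase only. Call the sites that take the Part B sentinel group X and those that take the Part A remainder Y.

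- If the Part A sentinel group is at X and the Part B remainder at Y, each Part is 12/54 = 22% X and 42/54 = 78% Y: no difference.
- If the Part A sentinel group is at Y and the Part B remainder at X, Part A is all Y and Part B all X: complete separation.

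The text allows both, so no size follows from it.

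**The plan's power figure**

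Inputs from section 6.1.1: 15 evaluable per arm, SD 0.85 on log10 ID50, two-sided alpha 0.05. Noncentral t with 28 df and noncentrality δ/(SD × √(2/15)):

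- log10(11) = 1.041; 1.041/(0.85 × 0.365) = 3.36; power 89.9%.
- The exact 90% point is 11.03-fold, so the stated 11-fold reproduces. It assumes that the arms differ only in the factor compared.

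**Assumed Part shift, no dose effect**

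The shifts below are assumptions. Chance of p ≤ 0.05:

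| Part shift b | ID50 fold, 10^(0.85b) | Dose contrast 15 vs 15, t-test | Same, Wilcoxon (simulated) | One regimen pooled, 30 vs 15, t-test |
|---|---|---|---|---|
| 0 | 1.0 | 5.0% | 4.4% | 5.0% |
| 0.2 SD | 1.5 | 8.3% | 7.6% | 6.1% |
| 0.3 SD | 1.8 | 12.5% | 11.3% | 7.5% |
| 0.5 SD | 2.7 | 26% | 23.8% | 12% |

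For b = 0.3 the noncentrality is 0.3/√(2/15) = 0.82 (28 df) for the dose contrast and 0.15/√(1/30 + 1/15) = 0.47 (43 df) for the half-pooled contrast. The last column ignores the small extra spread in the pooled arm (variance 1 + b²/4 = 1.02 at b = 0.3).

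In the other direction, if the shift opposes a true 1.1 SD dose effect, t-test power falls from 83% to 66% (0.2 SD) or 56% (0.3 SD).

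**The pooling gate**

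With 15 per arm and no Part shift, a true dose effect of 0.5 SD is non-significant 74% of the time. Passing the gate is therefore weak evidence that the doses respond alike.

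**The case against.** The strongest reply is that this is ordinary dose escalation, openly described. Sequential Parts follow from the sentinel safety reviews. The plan nowhere calls the dose comparison randomised, the comparison is secondary, and baseline characteristics will be tabulated by arm (section 6.3.2). All of that stands, and the design needs no change. But a descriptive table does not tell a reader how to take the dose p-values, and section 6.3.4.1 does not separate them from the randomised ones.

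A second reply is that the supplied SAP covers safety only, while protocol section 6.3.4.2 defers assay detail to a SAP. An adjustment could sit in a document not seen here. That limits the point to the supplied documents. Their only covariates for immunogenicity are predictors of missing outcomes, in the missing-data and repeated-measures models.

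Third, pooling is optional, section 6.3 says that unpooled comparisons will also be considered, and the worked example pools both regimens. This is fair, but the rule in section 6.3.4.1 still permits pooling one regimen alone.

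A reader might also infer more than the documents support:

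- That the primary comparisons are confounded with Part. They are not; all four are within Part.
- That any pooling over dose is biased. Pooling both regimens stays balanced.
- That the Parts enrol at different sites throughout. The split is stated for one phase, and the site mix could end up identical.
- That selection for FNA or leukapheresis is known to shift responses. Core eligibility is common to both Parts, up to 27 of 54 in Part A may decline both procedures, and nothing in the documents links willingness to antibody response.

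**Conclusion.** The point holds for the three between-dose comparisons and for any contrast between a pooled and an unpooled regimen. The former are observational comparisons of two separately randomised Parts. The latter would give up part of the protection that randomisation within Part provides.

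Neither the size nor the direction of a Part difference can be estimated from the documents. The rates of about 12% and 7.5% rest on an assumed shift of 0.3 SD, normal responses with equal variance, 15 evaluable per arm and no true dose effect. They show how sensitive the tests are, not that a bias of this size is expected. This is a gap in the analysis wording that should be closed, not a flaw in the design or in the primary immunogenicity analysis.

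**What to change.** In protocol section 6.3.4.1, carried into the SAP that governs immunogenicity:

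1. State that comparisons between dose levels are non-randomised because dose is set by Part, and that their p-values and intervals will be interpreted accordingly.
2. When aggregating over dose, pool both regimens in a contrast or neither, and stratify the test and the estimate by Part (for example a stratified Wilcoxon test, or a linear model with a Part term). Stratifying also handles unequal missing data between Parts. Ruling out one-sided pooling loses little: in a linear model with a Part term, the contrast of 2+5 vs 1 reduces to mean(2) minus mean(1), and Group 5 adds nothing to that estimate.
3. Add a sensitivity analysis of the dose contrasts adjusted for a few baseline variables already collected (SAP section 10.2 lists age, sex at birth and prior mRNA COVID-19 vaccination) and, where sites enrolled in both Parts, for site.

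Part cannot be a covariate in a dose contrast because it coincides with dose. Item 3 removes only what the measured variables carry; it does not remove enrolment period or willingness for the procedures, which is why item 1 is needed regardless.

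The cost is a few sentences and a little more analysis. The sensitivity analysis will be imprecise at about 15 evaluable per arm and should remain secondary. Enrolment, dosing and sample size are unchanged.

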6.1.1 Power calculations for immunogenicity

The immunogenicity sample size calculations allow for a 15% rate of missing immunogenicity data at Month 6.5. Of the n=18 enrolled per arm, we assume n=15 will be available for analysis.

A primary objective is to evaluate the ability of the BG505 MD39.3 trimer mRNA vaccines to elicit autologous neutralizing antibodies. The primary endpoint will be the occurrence and magnitude of serum antibody neutralization of pseudoviruses (BG505 T332N) as measured by the TZM-bl assay two weeks after the third vaccination which will be compared between the membrane-bound vaccine regimen (BG505 MD39.3 gp151 mRNA) and the membrane-bound knockout (BG505 MD39.3 gp151 CD4KO mRNA) and between the membrane-bound vaccine regimen (BG505 MD39.3 gp151 mRNA) and the soluble trimer (BG505 MD39.3 mRNA) vaccine arms, within each dose level. Secondary analyses will test for differences between dose levels. If no significant difference is seen between the 100mcg and 250mcg dose (eg, between Groups 1 and 4, between Groups 2 and 5 or between Groups 3 and 6), secondary analyses may aggregate over dose groups for comparisons between the vaccine regimens. For example, if no significant difference is seen between doses for the soluble trimer regimen in Groups 1 and 4 or between doses for the membrane-bound vaccine regimen in Groups 2 and 5, we may aggregate over the dose to compare responses of Groups 1 and 4 (n=30) to Groups 2 and 5 (n=30).

The precision with which the true immune response rate can be estimated from the observed data depends on the true underlying response rate and the sample size. Two-sided 95% confidence intervals for the response rate based on observing a particular rate of responses in the vaccinees is shown in [Table 6-1](#). Calculations are done using the score test method (29).

Table 6-1 Two-sided 95% confidence intervals for the true response rate based on observing a particular rate of responses in the vaccinees (n = 15, 30)

No. of responses	Observed response rate (%)	95% Confidence interval
4/15	26.7	(9.0, 51.9)
7/15	46.7	(24.8, 69.9)
11/15	73.3	(48.0, 89.1)
12/15	80.0	(54.8, 93.0)
8/30	26.7	(14.2, 44.4)
15/30	50.0	(33.2, 66.8)
22/30	73.3	(55.6, 85.8)
24/30	80.0	(62.7, 90.5)

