As shown in [Table 6-2](#), there is limited power for a formal comparison of immunogenicity response rates between vaccine arms of size n = 15. For either 80% or 90% power, the sizes of differences that the trial is powered to detect are large. These calculations use a Fisher's exact 2-sided test with a Type I error rate of 0.05. The trial is, however, adequately powered to detect group differences based on data from a study in rabbits led by [name]. There is 90% power to detect an 11-fold difference in ID50 pseudovirus neutralization and a 1.9-fold difference in serum binding responses between two dose groups or between two dose levels of n=15 evaluable samples each. For the comparisons of BG505 MD39.2 gp151 mRNA vs. BG505 MD39.3 mRNA (or vs. BG505 MD39.3 gp151 CD4KO mRNA) that aggregate arms over the low and high dose levels, the trial has 90% power to detect a 5.2-fold difference in ID50 pseudovirus neutralization and a 1.6-fold difference in serum binding responses between two groups, aggregated over dose level (n=30 evaluable samples in each of the aggregated groups). These calculations use a two-sided t-test with a Type I error rate of 0.05 and estimated standard deviation of 0.85 for log10 ID50 values and of 0.23 for ELISA AUC MD39 at day 182 (shown in [Figure 6-2](#)). The standard deviation estimates were based on the mean standard deviation across four groups of rabbits, with n=6 per group, given either soluble or membrane-bound MD39.3 or MD39.2 vaccine at 2 weeks after 3rd vaccination.

Table 6-2 Power for comparison of response rates between 2 arms (n1 = n2 = 15)

True response rate Arm 1 (%)	Minimum true response rate in Arm 2 in order to detect a difference	
	80% power	90% power
10	64	71
20	76	82
30	85	90
40	92	95
50	97	99

[figure not shown]

Figure 6-2 Effect size necessary to detect a difference between groups for n=3 to 20 per group.
Estimated standard deviation of \log_{10} ID50 values from day 182 is 0.85 (left). Estimated standard deviation of ELISA AUC MD39 is 0.23 (right). The two figures are identical except for the y-axis scale which depends on the outcome-specific estimated standard deviation

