In addition, “generic” power calculations inform the power of the study to compare immune response magnitudes between arms. These presume a continuous immune response, transformed to a 1-standard deviation scale, and a mean shift in scaled immune response between arms. [Table 6-3](#) shows the power for comparing immune responses between two arms at Month 6.5 (n = 15 per arm, n = 30 per group). Note that the study is powered to detect moderate 1.1- standard deviation differences in immune responses between arms for n=15 per arm and to detect 0.8- standard deviation differences in immune responses between groups for n=30 per group.

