6.1.2 Power calculations for safety

The goal of the safety evaluation for this study is to identify safety concerns associated with vaccine administration. The ability of the study to detect SAEs can be expressed by the true event rate above which at least one SAE would likely be observed and the true event rate below which no events would likely be observed. Specifically, with n=4 in the sentinel safety group for a given arm, there is at least 90% chance of observing at least one safety event among those 4 if the true rate of such an event is 45% or more; and there is at least a 90% chance of observing no events among the 4 if the true rate is 2.5% or less. Safety calculations are evaluated using historical controls. As a reference, in HVTN vaccine trials conducted in the US from April 2008 through March 2018, about 1% of participants who received placebos experienced an SAE.

Table 6-3 Power for comparing the magnitude of a generic immune response between arms.

Immune responses are compared using 0.025-level one-sided Wilcoxon rank sum tests.

Continuous immune responses are assumed to follow a normal distribution, transformed to a 1-standard deviation scale, with a mean of zero in one arm and the same standard deviation in the two arms. To allow for missing immunogenicity data, analyses include 15 participants in each arm and 30 participants if aggregating over dose level in Part A and Part B. Power is based on 5000 simulations.

Mean difference between arms (in standard-deviation units)	Power, n=15 per arm	Power, n=30 per group (aggregating over dose)
0.8 SD	51%	84%
0.9 SD	63%	91%
1.0 SD	71%	96%
1.1 SD	80%	98%
1.2 SD	86%	100%
1.3 SD	91%	100%

Binomial probabilities of observing 0, 1 or more events among the n=4 sentinel participants receiving each study vaccine are presented in [Table 6-4](#) for a range of possible true adverse event rates. Probabilities are also provided for the total safety sentinel group for each dose group (n=12) as well as for each vaccine arm (n=18). These calculations provide a more complete picture of the sensitivity of this study design to identify potential safety problems with the vaccine.

Table 6-4 Probability of observing 0 events, 1 or more events among arms of n=4, 12, 18 for different true event rates

True event rate (%)	arm size	0 events	1+ events
10	4	0.66	0.34
20	4	0.41	0.59
30	4	0.24	0.76
10	12	0.28	0.72
20	12	0.07	0.93
30	12	0.01	0.99
10	18	0.15	0.85
20	18	0.02	0.98
30	18	0	1

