6.3.4 Immunogenicity analyses

6.3.4.1 General approach

For the statistical analysis of immunogenicity endpoints, data from enrolled participants will be used according to the initial randomization assignment regardless of how many injections they received. Additional analyses may be performed, limited to participants who received all scheduled injections per protocol. Assay results that are unreliable are excluded; results from specimens collected outside of the visit window, or from HIV-infected participants post-infection, may be excluded. Since the exact date of HIV infection is unknown, any assay data from blood draws 4 weeks prior to an infected participant's last seronegative sample and thereafter may be excluded. If an HIV-infected participant does not have a seronegative sample postenrollment, then all data from that participant may be excluded from the analysis.

Discrete categorical assay endpoints (eg, response rates) will be analyzed by tabulating the frequency of positive response for each assay by antigen and treatment arm at each timepoint for which an assessment is performed. Crude response rates will be presented with their corresponding 95% confidence interval estimates calculated using the score test method (40). Barnard or Fisher's exact tests, as specified in the SAP, will be used to compare the response rates of any 2 vaccine arms, with a significant difference declared if the 2-sided p-value is ≤ 0.05 . In general Barnard's is preferred since under most circumstances it is more powerful than Fisher's exact test (41).

For quantitative assay data (eg, percentage of positive cells from ICS assay), graphical and tabular summaries of the distributions by antigen, treatment arm, and timepoint will be made. For all primary and secondary immunogenicity endpoints, box plots and plots of estimated reverse cumulative distribution curves will be used for graphical display of all of the study arms. Typically, the results will be shown for each vaccine arm.

The difference between arms at a specific timepoint will be tested with a nonparametric Wilcoxon rank sum test if the data are not normally distributed and with a 2-sample t-test if the data appear to be normally distributed. The primary

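### Part A is randomised within strata of willingness for FNA and/or leukapheresis, but the tests named for its two primary magnitude contrasts do not use the stratum; they stay valid and may give up some power

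*Protocol*

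**What the plan says.** Protocol section 6.2 sets the design: "Randomization to Groups 1-3 will be stratified by willingness to consent to FNA and/or leukapheresis". It adds a cap: "A maximum of 27 participants in total that do NOT consent to either FNA and leukapheresis collection will be enrolled". SAP section 7 repeats both. No stratification factor is named for Part B, where "the remaining Part B participants (n=42) will be enrolled with 1:1:1 randomization".

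For quantitative assay data, Protocol section 6.3.4.1 says that the difference between arms "will be tested with a nonparametric Wilcoxon rank sum test" if the data are not normal, and with a two-sample t-test if they appear normal. It lists four primary contrasts. Two lie in Part A (Group 2 vs 1, Group 2 vs 3) and two in Part B (Group 5 vs 4, Group 5 vs 6). Response rates are compared by Barnard's or Fisher's exact test, with Barnard's generally preferred. None of these tests is described with a stratum term, and no reason is given for leaving the stratum out.

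On sample size, section 6.1.1 says: "Of the n=18 enrolled per arm, we assume n=15 will be available for analysis". It also says that "the study is powered to detect moderate 1.1- standard deviation differences in immune responses between arms for n=15 per arm". Table 6-3 gives 80% power for that case.

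**The concern.** Randomising within strata balances Groups 1-3 on the stratum, so differences between strata largely drop out of the arm difference. An unstratified test still counts those differences as noise. If the stratum is related to response, its standard error is too large, its true type I error falls below the nominal level, and power is lost. With about 15 evaluable per arm there is little power to spare. Section 6.1.1 itself calls the power to compare response rates limited.

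Leaving the stratum unmentioned also leaves the choice between an adjusted and an unadjusted result open until the data are in hand, in an open-label trial.

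**Working it through.** **Inputs from the documents.** 15 evaluable of 18 per arm (section 6.1.1); shift of 1.1 SD (section 6.1.1, Table 6-3); two-sided 0.05, because the Table 6-3 caption says: "Immune responses are compared using 0.025-level one-sided Wilcoxon rank sum tests".

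**Assumed inputs.** Split between strata: if the cap of 27 applies to the 54 Part A participants (3 × 18), non-consenters are at most half, so 8/7 of 15 is used, with 10/5 as a check. Stratum effect D, the difference in mean response between strata: not in the documents, so 0 to 1.0 SD is shown. Outcomes are normal.

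**Step 1: reproduce the plan.** An unstratified Wilcoxon simulation (40,000 runs, continuity-corrected normal approximation) at n = 15 gives 52.5, 62.3, 71.5, 79.5, 86.1 and 91.2% for shifts of 0.8 to 1.3 SD. Table 6-3 states 51, 63, 71, 80, 86 and 91%. The protocol also says: "There is 90% power to detect an 11-fold difference in ID50 pseudovirus neutralization". There, log10(11)/0.85 = 1.225 SD, and the noncentral t with 28 df and noncentrality 1.225 × √(15/2) = 3.355 gives 89.9%. Both figures reproduce.

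**Step 2: the mechanism.** With arms balanced within strata and within-stratum SD σ, the variance of the arm difference is 2σ²/n. The unstratified t-test estimates about 2(σ² + p(1−p)D²)/n. For an 8/7 split, p(1−p) = 56/225 = 0.249. With σ = 1, the standard error is too large by √(1 + 0.249 × 0.25) = 1.03 at D = 0.5 and by √1.249 = 1.12 at D = 1.0.

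**Step 3: the comparison.** The unstratified tests were set against two stratum-based ones:
- Van Elteren: sum over strata of w(R − k(2k+1)/2), with k per arm in the stratum, R the rank sum, w = 1/(2k+1) and variance Σw²k²(2k+1)/12.
- Linear model with arm and stratum (27 residual df).

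Results for 40,000 runs, 8/7 split, within-stratum SD 1, power at a shift of 1.1 SD:

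| D (SD) | Wilcoxon power | van Elteren power | t power | linear model power | Wilcoxon type I | van Elteren type I |
|---|---|---|---|---|---|---|
| 0 | 79.3% | 78.8% | 82.6% | 82.6% | 4.5% | 4.8% |
| 0.25 | 78.9% | 79.1% | 82.2% | 82.5% | 4.4% | 4.8% |
| 0.5 | 77.5% | 79.0% | 81.1% | 82.7% | 4.0% | 5.0% |
| 1.0 | 71.5% | 79.3% | 75.9% | 82.9% | 2.5% | 4.8% |

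Monte Carlo standard error is about √(0.79 × 0.21/40,000) = 0.2 points for power. The Wilcoxon loss is 79.0 − 77.5 = 1.5 points at 0.5 SD and 79.3 − 71.5 = 7.8 points at 1.0 SD. A separate run at 0.3 SD gave 79.0 vs 79.1%, so nothing is lost there. With a 10/5 split the loss is 79.1 − 77.8 = 1.3 points at 0.5 SD and 79.2 − 72.3 = 6.9 points at 1.0 SD.

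**Step 4: the reading of the planning SD.** If the total SD is held at 1 instead, Wilcoxon vs van Elteren power is 79.6 vs 79.0% (D = 0), 79.9 vs 81.3% (0.5) and 81.4 vs 89.2% (1.0). On this reading the planned test still meets the stated 80%.

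**Step 5: response rates.** Exact power at n = 15 per arm, 8/7 split, no stratum effect, Barnard's test vs the conditional stratified exact test:
- 10 vs 64%: 89.6 vs 81.9%
- 20 vs 76%: 89.7 vs 80.9%
- 30 vs 85%: 89.0 vs 80.3%

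The stratified test loses 7.7 to 8.8 points. Its true type I error is about 2%, against about 4% for Barnard's.

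**The case against.** The strongest reply is that the harm is hypothetical. The protocol introduces the subset to obtain lymph node samples and large cell numbers (sections 2.6, 2.7, 8.5). The extra criteria in section 5.1.3 concern venous access, bleeding risk, anaesthetic allergy, local conditions and pheresis-centre rules. None is presented as a predictor of neutralisation. This stands. The documents do show that the strata differ in handling: under Appendix A, the Visit 8 and Visit 12 PBMC blood draws are taken only from participants who do not have leukapheresis. That bears on the T-cell endpoint more than on serum neutralisation.

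A reader might infer that every arm comparison in the trial ignores the stratum. The documents do not support that. Part B has no stated stratum. The models in section 6.3.4.1 for more than 20% missing data and for repeated measures take baseline predictors of the missing outcomes, so the stratum could enter there. The supplied SAP covers safety only (SAP section 2), so an immunogenicity SAP may say more.

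A reader might also infer that the tests are invalid, or that the stated power is wrong. Neither follows: type I error is not inflated, and Step 4 shows that 80% still holds if the planning SD is a total SD. The protocol does not say which SD is meant.

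Finally, it is tempting to stratify the response-rate test too. Step 5 shows that this costs power. Barnard's test stays ahead even with a 20-point stratum difference in response rate (for example 89.8 vs 85.8%).

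**Conclusion.** The point holds as one of efficiency and prespecification for two contrasts, the magnitude comparisons of Group 2 vs 1 and Group 2 vs 3. The tests named for them do not use the factor on which Part A was randomised. They are valid, and conservative if the stratum predicts response. The loss is about zero for stratum effects up to 0.3 SD, about 1.5 points at 0.5 SD and about 8 points at 1.0 SD, where Wilcoxon type I error is about 2.5%. These sizes rest on an assumed stratum effect, a near-even split, normal outcomes and a within-stratum SD of 1. The cap of 27 is a maximum, so the split may be less even and the loss smaller: with 12/3 it is 0.9 points at 0.5 SD. Whether the stratum affects neutralisation at all cannot be told from the documents.

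**What to change.** For the magnitude comparisons of Group 2 vs 1 and Group 2 vs 3, name the van Elteren stratified rank-sum test, or a linear model with arm and stratum on the t-test route, with the randomisation stratum as the factor. Keep Barnard's test for response rates. Leave Group 5 vs 4 and Group 5 vs 6 unstratified. The optional dose-pooled comparisons mix the two parts; they were not examined here and this change does not cover them.

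This is a change of analysis wording, best made before the Month 6.5 data are analysed. It uses a variable needed for the randomisation and requires no new data or participants. The statistical cost is under 1 power point if the stratum has no effect (79.3 vs 78.8% in Step 3).
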